4.7 Adverse Events

The methods for collecting adverse events are described below.

4.7.1 Adverse Events

4.7.1.1 Definitions

The definitions of adverse events (AEs), serious adverse events (SAEs) and other significant adverse events (OAEs) are given below. It is of the utmost importance that all staff involved

in the study are familiar with the content of this section. The principal investigator is responsible for ensuring this.

Adverse event

An adverse event is the development of an undesirable medical condition or the deterioration of a pre-existing medical condition following or during exposure to a pharmaceutical product, whether or not considered causally related to the product. An undesirable medical condition can be symptoms (eg, nausea, chest pain), signs (eg, tachycardia, enlarged liver) or the abnormal results of an investigation (eg, laboratory findings, electrocardiogram). In clinical studies, an AE can include an undesirable medical condition occurring at any time, including run-in or washout periods, even if no study treatment has been administered.

Serious adverse event

A serious adverse event is an AE occurring during any study phase (ie, run-in, treatment, washout, follow-up), and at any dose of the investigational product, comparator or placebo, that fulfils one or more of the following criteria:

- results in death
- is immediately life-threatening
- requires in-patient hospitalization or prolongation of existing hospitalization
- results in persistent or significant disability or incapacity
- is a congenital abnormality or birth defect
- is an important medical event that may jeopardise the subject or may require medical intervention to prevent one of the outcomes listed above.

The causality of SAEs (ie, their relationship to study treatment) will be assessed by the investigator(s), who in completing the relevant case report form must answer “yes” or “no” to the question “Do you consider that there is a reasonable possibility that the event may have been caused by any of the following – study medication – other medication?” For further guidance on the definition of a SAE and a guide to the interpretation of the causality question, see Appendix B to the Clinical Pharmacology Study Protocol.

Other Significant Adverse Events (OAE)

OAEs will be identified by the Drug Safety Physician and if applicable also by the Clinical Study Team Physician during the evaluation of safety data for the Clinical Study Report. Significant adverse events of particular clinical importance, other than SAEs and those AEs leading to discontinuation of the subject from study treatment, will be classified as OAEs. Examples of these are marked haematological and other laboratory abnormalities, and certain events that lead to intervention (other than those already classified as serious), dose reduction

or significant additional treatment. For each OAE, a narrative may be written and included in the Clinical Study Report.

4.7.1.2 Recording of adverse events

The subjects will be told to report any AE occurring during the study to the investigator or his personnel. Open standardized AE questioning, such as “Have you had any health problems since the previous visit?” will be done by the investigators or their personnel at each contact with the subject. The AE open standardized questioning should be done discretely in order to prevent the subjects from influencing each other.

Any AEs observed or reported by a subject and/or staff, will be recorded in the CRF. Any AE including clinical findings not resolved at the follow-up visit, will be followed up at an additional visit or telephone contact within 7 days after the follow-up visit or until resolved or explained.

Laboratory and vital sign abnormalities will not be recorded as an AE unless any criterion for an SAE is fulfilled, the subject discontinues the study due to the result(s), or the investigator insists that it should be reported as an AE. If a laboratory value or vital sign is associated with clinical signs and symptoms, the signs and symptoms should be reported as an AE and the associated laboratory or vital signs should be considered additional information. Any sign or symptom that fulfills the SAE definition (Appendix B) or is the reason for discontinuation of treatment of investigational products should be reported accordingly.

The following variables will be recorded for each AE noted:

- Onset, resolution
- Intensity (mild/ moderate/ severe)
- Action(s) taken
- Outcome of the AE
- Causality of the AE (yes or no)
- Whether it constitutes an SAE or not

The intensity rating is defined as:

1 = mild (awareness of sign or symptom, but easily tolerated)

2 = moderate (discomfort sufficient to cause interference with normal activities)

3 = severe (incapacitating, with inability to perform normal activities)

It is important to distinguish between serious and severe AEs. Severity is a measure of intensity whereas seriousness is defined by the criteria in Section 4.7.1.1. An AE of severe intensity need not necessarily be considered serious. For example, nausea that persists for several hours may be considered severe nausea, but not a SAE. On the other hand, a stroke that results in only a limited degree of disability may be considered a mild stroke but would be a SAE.

4.7.1.3 Reporting of serious adverse events

Investigators and other site personnel must inform appropriate AstraZeneca representatives of any SAE that occurs in the course of the study within 1 day (ie, immediately but no later than the end of the next business day) of when he or she becomes aware of it.

The AstraZeneca representative will work with the investigator to compile all the necessary information and ensure that the appropriate AstraZeneca Drug Safety Department receives a report by day one for all fatal and life-threatening cases and by day five for all other SAEs.

Follow-up information on SAEs must also be reported by the investigator within the same time frames.

If a non-serious AE becomes serious, this and other relevant follow-up information must also be provided to AstraZeneca within 1 day as described above. For a non-serious AE that become serious but which is not fatal or life-threatening a report should be received within 5 days.

All SAEs have to be reported, whether or not considered causally related to the investigational product or to the study procedure(s). All SAEs will be recorded in the case report form. The investigator is responsible for informing the Ethics Committee and/or the Regulatory Authority of the SAE as per local requirements.

5. STUDY MANAGEMENT

5.1 Monitoring

5.1.1 Study monitoring

The monitoring of this study will be performed in accordance with the principles of Good Clinical Practice (GCP) as laid out in the International Conference on Harmonization (ICH) document “Good Clinical Practice: Consolidated Guideline”.

The specific requirements of the genetic part of the study will be discussed with the investigator(s) (and other personnel involved with the study).

5.1.2 Data verification

It is a prerequisite of this study that the study monitor has direct access to source data for data verification. This will be done by comparing data from the pCRFs with those in the subject's

medical notes (permission from the subject will be sought as part of the consent process). Such verification is an essential element of quality control, as it allows the rectification of transcription errors and omissions.

Monitoring including source data verification should routinely be performed prior to the transfer of data to Data Management.

Source verification of the genetic consent of participating subjects will be performed and make sure that the investigational team is adhering to the specific requirements of the genetics aspects of the study.

5.1.3 Archiving of study documentation

AstraZeneca will retain all documentation pertaining to this study in AstraZeneca for central file for as long as AZD6140 is available for human consumption..

The investigator will retain all documentation pertaining to this study for at least 15 years.

5.2 Audits and inspections

Authorized representatives of AstraZeneca, a regulatory authority, an Independent Ethics Committee (IEC) or an Institutional Review Board (IRB) may visit the centre to perform audits or inspections, including source data verification. The purpose of an AstraZeneca audit or inspection is to systematically and independently examine all study related activities and documents to determine whether these activities were conducted, and data were recorded, analysed, and accurately reported according to the protocol, GCP guidelines of the ICH and any applicable regulatory requirements. The investigator should contact AstraZeneca immediately if contacted by a regulatory agency about an inspection at his or her centre.

5.3 Training of staff

The principal investigator will maintain a record of all individuals involved in the study (medical, nursing and other staff). He or she will ensure that appropriate training relevant to the study is given to all of these staff, and that any new information of relevance to the performance of this study is forwarded to the staff involved.

Before the first subject is entered into the study the investigational staff will have an opportunity to discuss the procedures associated with the collection of blood samples, extraction of DNA and genetic testing with AstraZeneca personnel. The ethical considerations specific to genotyping and the importance of the informed consent process will be made clear. The requirements for the collections of the subjects' sample will also be made clear.

5.4 Changes to the protocol

Study procedures will not be changed without the mutual agreement of the principal investigator and AstraZeneca.

If it is necessary for the study protocol to be amended, the amendment and/or a new version of the study protocol must be notified to or approved by each IEC or IRB, and in many countries also the local regulatory authority, before implementation. Local requirements must be followed.

If a protocol amendment requires a change to a particular centre's Master Informed Consent Form, then AstraZeneca and the centre's IEC or IRB must be notified. Approval of the revised Master Informed Consent Form by AstraZeneca and by the IEC or IRB is required before the revised form is used.

AstraZeneca will distribute amendments and new versions of the protocol to each principal investigator(s) who in turn is responsible for the distribution of these documents to his or her IEC or IRB, and to the staff at his or her centre. The distribution of these documents to the regulatory authority will be handled according to local practice.

5.5 Study agreements

The principal investigator at each centre must comply with all the terms, conditions, and obligations of the study agreement for this study. In the event of any inconsistency between this protocol and the study agreement, this protocol shall prevail.

Specific reference to genetics should be included in the agreement. The contractual obligations should not include any additional payment for collecting the samples, unless special processing is required.

5.6 Study timetable and end of study

The study is expected to start in October 2004 and to be completed by December 2004.

5.7 Data management

5.7.1 Case report forms

Paper CRFs (pCRFs) will be used to record all data not captured electronically. Data should be recorded legibly onto the pCRFs in blue or black ballpoint pen. Correction fluid or covering labels must not be used.

The AstraZeneca Monitor will check data at the monitoring visits to the investigational site. The Investigator will ensure that the data in the pCRFs are accurate, complete and legible.

Data from the completed pCRFs will be entered onto AstraZeneca's clinical study database and validated under the direction of the Data Manager. Any missing, impossible or inconsistent recordings in the pCRFs will be referred back to the Investigator using a data query form (DQF), and be documented for each individual subject before clean file status is declared.

5.7.2 Pharmacogenetic data

In the case of genotypic data, only the date the subject gave consent to participation in the genetic component of the study and the date the blood sample was taken from the subject will be recorded in the pCRF and database.

The genotypic data generated from the study will be stored in the AstraZeneca LIMS database or other appropriate system. This database is a secure database, which is separate to the clinical database. Some or all of the clinical study dataset may be duplicated within the AstraZeneca LIMS database for exploratory genetic analysis.

However, some or all of the clinical study dataset may be duplicated within the AstraZeneca LIMS database or other appropriate system for exploratory analysis.

5.8 Reporting of Genotypic Results

Results from any genetic research performed will be reported separately from the clinical trial report. AstraZeneca will not provide individual genotype results to subjects, their family members, any insurance company, an employer, clinical study investigator, general physician or any other third party, unless required to do so by law. The subject's DNA will not be used for any purpose other than those described in the study protocol.

Individual subjects will not be identified in any report or publication resulting from this work. The data and results of this study may be reviewed with collaborators and published, but neither the subject's name nor any other personal identifiers will appear in any publication or report.

6. PHARMACOKINETIC, PHARMACODYNAMIC, SAFETY, GENETIC AND STATISTICAL METHODOLOGY

6.1 Pharmacokinetic / pharmacodynamic evaluation

6.1.1 Calculation or derivation of pharmacokinetic variables

The pharmacokinetic analyses will be performed by Clinical Pharmacokinetics, Experimental Medicine, AstraZeneca, Wilmington, DE. To be followed by a description of each pharmacokinetic variable to be included in the analysis and the means by which each is calculated.

Plasma concentrations of AZD6140 and its metabolite AR-C124910XX will be listed and depicted graphically as a function of time relative to Day 1 dose for the 3 cohorts. Pharmacokinetic parameters listed below will be estimated by non-compartmental analysis.

Day 1: C_{max} , t_{max} , AUC_{0-12} of AZD6140 and AR-C124910XX, metabolite to parent C_{max} and AUC ratios

Day 4: C_{max} , t_{max} , AUC_{τ} , metabolite to parent C_{max} and AUC ratios of AZD6140 and AR-C124910XX and, AZD6140 steady state CL/F.

AZD6140 and AR-C124910XX C_{max} will be estimated as the highest measured concentration and t_{max} will be the time to maximum concentration within a dosing interval on Days 1 and 4. AUC_{0-12} and AUC_{τ} will be calculated using the linear trapezoidal method over the 12 hour dosing interval on Days 1 and 4, respectively. AZD6140 CL/F will be estimated as the ratio of AZD6140 dose and AUC_{τ} on Day 4. The ratio of AR-124910XX C_{max} to AZD6140 C_{max} ratio and, AR-124910XX AUC to AZD 6140 AUC ratio will be calculated on Days 1 and 4.

6.1.2 Calculation or derivation of pharmacodynamic variables

Changes from baseline in each period for respiratory parameters will be calculated.

6.1.3 Calculation or derivation of pharmacokinetics/pharmacodynamics

Relationship between AZD6140 concentration and PD endpoints will be explored graphically.

6.2 Safety evaluation

6.2.1 Calculation or derivation of safety variables

Changes from baseline for the safety data (adverse events, vital signs, 12-lead ECG, physical examination data, laboratory data) will be calculated.

6.3 Genetics as a co-variate (not applicable)

6.4 Statistical methods and determination of sample size

6.4.1 Statistical evaluation

A comprehensive Statistical Analysis Plan (SAP) will be prepared and finalized before database lock. The goal of this analysis is to assess the effect of AZD6140 on the respiratory parameters in healthy volunteers, mild asthma patients and mild COPD patients.

6.4.2 Description of analysis sets

6.4.2.1 Pharmacodynamic analysis set

All subjects who have evaluable respiratory measurements in both periods of the study without any protocol deviations/violations deemed to affect the pharmacodynamics of AZD6140 will be included in the summaries and listings of the pharmacodynamic data.

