3. STUDY PLAN AND PROCEDURES

3.1 Overall study design

This will be a randomized, double blind, placebo-controlled, 3 cohort PK/PD, single center study to assess the effect of AZD6140 on respiratory parameters in healthy volunteers, mild asthmatic and COPD patients between 55 to 75 years of age.

Up to 12 men or women (non childbearing potential) will be randomized in each cohort to ensure the completion of at least 8 subjects within each cohort.

Cohort	Volunteer Type	Respiratory criteria	Number subjects
A	Healthy	N/A	8
B	Mild Asthmatic	FEV ₁ > 70%; no exacerbation in past 8 weeks; reversibility demonstrated within the past year (\geq 12% or 200 mL)	8
C	Mild COPD	FEV ₁ \geq 60%; no exacerbations in past 8 weeks; history of tobacco smoking > 10 pack years	8

On Study Day 1 of Period I, each subject will receive one of the following treatments according to the randomization schedule:

Treatment A: A single, oral dose of 450 mg AZD6140 (5 x 90 mg immediate release tablets) will be administered in the AM of Study Day 1; followed by a single, oral dose of 180 mg AZD6140 (2 x 90 mg immediate release tablet) in the PM (12 hours after the first dose); thereafter, 180 mg AZD6140 (2 x 90 mg immediate release tablet) will be administered bid (every 12 hours) on Study Days 2 and 3 and in the AM only on Study Day 4.

Treatment B: A single, oral dose of AZD6140 matching placebo (5 placebo tablets) will be administered in the AM of Study Day 1; followed by a single, oral dose of AZD6140 matching placebo (2 placebo tablets) in the PM (12 hours after the first dose); thereafter, AZD6140 matching placebo (2 placebo tablets) will be administered bid (every 12 hours) on Study Days 2 and 3 and in the AM only on Study Day 4.

At the end of Period I, all subjects will crossover to receive the alternate treatment following a 7 – 10 day washout period. During each treatment period, pharmacodynamic measurements and safety variables will be assessed. Blood samples will be collected for analysis of AZD6140 and its metabolite, AR-C124910XX.

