The optional genetic sampling will be taken from subjects who have signed a separate consent form for genetic analysis on Study Day 1 prior to dose administration (Period I only). Blood samples for the determination of AZD6140, and its metabolite AR-C124910XX, in plasma will be collected on Study Days 1, 2, 3 and 4 in each treatment. Refer to Table 2 , Table 3 and Sections 4.3 and 4.4 for the timing and detailed descriptions of all the study procedures and assessments to be performed in each treatment.

If a subject experiences a spontaneous dyspnea episode any time throughout the inpatient study period (beginning with first dose administration), specific study procedures need to be completed sequentially as described in Table 3. These procedures should be completed at the onset of each dyspnea episode with the exception of an occurrence during cycle exercise testing.

If a dyspnea episode manifests intermittent symptoms within short time intervals (hours), generally if symptoms are similar and no initial abnormalities are observed on assessments, repeat assessments may be performed as needed at the investigator's judgement to monitor the subject's condition. Other diagnostic studies, such as echocardiogram or chest x-ray, may be performed to evaluate dyspnea at the investigator's discretion.

If a dyspnea episode subjectively worsens, assessments should be repeated at the investigator's discretion. The subject's dyspnea should resolve, or return to subject's baseline, before subject proceeds on to Period II (see Section 3.3.5.1).

Subjects will be discharged from the study center on Study Day 5 , after the completion of all protocol-driven procedures and assessments and at the discretion of the investigator. At discharge, subjects will be reminded of the study restrictions listed in Section 3.3.4 and instructed when to return for admission to Period II.

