This will be a double-blind, randomized, placebo-controlled, 2-period crossover, 3 cohort, pharmacodynamic study. Healthy volunteers are included as well as patient population (mild asthma and COPD patients) so that qualification of the differences in physiologic response and subjective experience of dyspnea can be compared to a healthy population.

Asthma and COPD patients are included primarily to ascertain if the physiologic response differs from healthy volunteers as this observation was only observed in a patient population and not in healthy volunteers in Phase I studies. Additionally, examining any dyspnea effects in COPD and asthma patients as compared to healthy volunteers will help to establish safety parameters. Healthy volunteers will be studied first to increase safety. The age range encompasses that of the Phase II study where dyspnea was first observed. Mild disease patients are chosen to minimize impact on any underlying disease state.

The primary variable will be respiratory rate and minute ventilation, based on the hypothesis of affecting adenosine receptors and preclinical observations. Cardiopulmonary exercise testing is included because provocation of the system may elicit measurable changes in physiological parameters that are not otherwise observed. Exercise testing also provides an opportunity to simulate the conditions that could contribute to dyspnea during daily activities.

A loading dose of 450 mg is chosen to maximize the potential of eliciting dyspnea. This dose will establish safety margins for a clinical loading dose that may be up to 270 mg. Dosing to 3 days will allow for attainment of steady-state plasma concentrations. Again, this will provide for assessment of dyspnea under clinically relevant conditions. A placebo crossover will be performed because dyspnea is a highly subjective sensation, and therefore comparison to a placebo baseline is desirable.

A retrospective genetic analysis to explore the genetic variables in genes that are important to absorption and disposition of, and response to AZD6140 may be carried out. Genetic sampling will be optional to all subjects enrolled. Subjects will receive the same treatment and care in the main study whether or not subjects donate a blood sample for genetic research. The genetic data from this study may be pooled with genetic results from other studies on AZD6140 to generate hypotheses to be tested in future studies.

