3.3.5 Discontinuation of subjects from treatment or assessment

3.3.5.1 Criteria for discontinuation

Subjects may be discontinued from study treatment and assessments at any time. Specific reasons for discontinuing a subject from this study are:

- Voluntary discontinuation by the subject, who are at any time free to discontinue their participation in the study without prejudice to further treatment
- Safety reasons as judged by the investigator and/or AstraZeneca including moderate to severe dyspnea that does not resolve or return to subject's baseline within 2 weeks.
- Severe non-compliance to protocol as judged by the investigator and/or AstraZeneca.
- Incorrect enrollment (ie, the subject does not meet the required inclusion/exclusion criteria) or randomization (ie, the subject is not allocated study drug as described in the protocol) of the subject.
- Subject lost to follow-up
- A suspected/manifested infection according to WHO risk categories 2, 3, and 4 (Refer to Appendix D).

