3.4.2 Doses and treatment regimens

Each subject will receive each of the following treatments in one of two treatment sequences (AB or BA) according to the randomization schedule:

Treatment A: A single, oral dose of 450 mg AZD6140 (5 x 90 mg immediate release tablets) will be administered in the AM of Study Day 1; followed by a single, oral dose of 180 mg AZD6140 (2 x 90 mg immediate release tablet) in the PM (12 hours after the first dose); thereafter, 180 mg AZD6140 (2 x 90 mg immediate release tablet) will be administered bid (every 12 hours) on Study Days 2 and 3 and in the AM only on Study Day 4.

Treatment B: A single, oral dose of AZD6140 matching placebo (5 placebo tablets) will be administered in the AM of Study Day 1; followed by a single, oral dose of AZD6140 matching placebo (2 placebo tablets) in the PM (12 hours after the first dose); thereafter, AZD6140 matching placebo (2 placebo tablets) will be administered bid (every 12 hours) on Study Days 2 and 3 and in the AM only on Study Day 4.

All doses given in each treatment will be administered with 240 mL of room temperature water while the subject is sitting in an upright or in a semi-recumbent position. Subjects must remain either sitting or semi-recumbent for at least 2 hours after each dose intake.

On Study Days 1 and 4 of each treatment, the subjects will receive the AM study medication following an overnight (10 hour) fast and will continue to fast for 4 hours post dose. The PM

dose on Study Days 1, 2 and 3 will be given either 1 hour before or 1 hour after food intake. On Study Day 2 and 3, breakfast will be served 1 hour after the AM study medication.

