3.4.3 Method of assigning subjects to treatment groups

Written informed consent will be obtained before enrollment and the volunteers identified with an enrollment number starting with E0001001. Subjects fulfilling the eligibility criteria will be assigned subject numbers starting with either number **101** (Cohort A), **201** (Cohort B) or **301** (Cohort C).

Using the AZ Global Randomization system (Grand) by AstraZeneca LP, volunteers treatment will be allocated as generated by the system.

Cohort	Volunteer Type	Randomization Number
A	Healthy Volunteers	101, 102, 103, 104, etc.
B	Mild Asthma	201, 202, 203, 204, etc.
C	Mild COPD	301, 302, 303, 304, etc.

Subjects will be randomized strictly sequentially within their Cohort as subjects are eligible for randomization on Day 1 of Period I before study drug administration. If a subject should be incorrectly randomized, randomization should continue with no attempt to correct the error. If a subject discontinues from the study, the randomization number will not be re-used and the subject will not be allowed to re-enter the study. Subjects who withdraw after having received study medication may be replaced by a subject who will be assigned to the same treatment sequence.

Each treatment group will consist of the same combination of matching active and placebo tablets. There will be four additional individual drug packages supplied for each cohort in the event of misrandomization, early withdrawal, etc. These will be used only as back-up and not for over enrolling subjects.

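### The both-periods pharmacodynamic set leaves AZD6140-first subjects who stop for dyspnea before Period II out of the primary respiratory summaries and listings

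*Protocol*

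**What the plan says.** Section 6.4.2.1 admits "All subjects who have evaluable respiratory measurements in both periods of the study without any protocol deviations/violations deemed to affect the pharmacodynamics" of AZD6140, and says that these subjects "will be included in the summaries and listings of the pharmacodynamic data". The rule therefore governs individual listings too. The neighbouring sets are wider: the pharmacokinetic set (6.4.2.2) has no both-periods condition, and the safety set (6.4.2.3) keeps everyone who took a dose.

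The set carries the primary objective. Section 3.2 states: "The primary variable will be respiratory rate and minute ventilation".

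Four other places decide who can reach the set:

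- Section 3.4.2: each subject is treated "in one of two treatment sequences (AB or BA) according to the randomization schedule", so some receive AZD6140 in Period I.
- Section 3.1.2: dyspnea should have settled "before subject proceeds on to Period II".
- Section 3.3.5.1: the safety reasons for discontinuation are described as "including moderate to severe dyspnea that does not resolve or return to" the subject's baseline within 2 weeks.
- Section 3.4.3: "Subjects who withdraw after having received study medication may be replaced by a subject who will be assigned to the same treatment sequence". Section 3.1 allows up to 12 randomized per cohort "to ensure the completion of at least 8 subjects within each cohort".

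**The concern.** The study exists to describe what AZD6140 does to breathing, and Section 3.2 says that the 450 mg loading dose was picked to give dyspnea its best chance of appearing. A subject who takes AZD6140 first and stops for dyspnea before Period II has respiratory measurements on active drug but none in the second period. Section 6.4.2.1 then removes those measurements from the summaries and the listings. If a replacement completes, the cohort display still shows eight subjects and nothing in it reveals the loss.

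Membership of the set thus depends on a symptom closely tied to the outcome. If those who stop have larger changes in respiratory rate or minute ventilation than those who continue, the described effect is too small. The comparison of sensitivity between healthy, asthma and COPD cohorts, which is the reason for Cohorts B and C, could also be blunted if stopping is more common in the patient cohorts.

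**Working it through.** The protocol gives no figure to reproduce: Section 6.4.4 bases the sample size on feasibility and states no dropout rate. The check has three steps.

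**1. Who is certainly lost**

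- AZD6140 first, stops before Period II: active-drug data exist, no second-period data. Excluded.
- Placebo first, stops during Period II: may already have measurements in both periods. Not clearly excluded, because the section does not say what makes a measurement evaluable.

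The certain loss is confined to the first group.

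**2. How many**

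Inputs: 3 cohorts of 8 = 24 subjects (synopsis). Assuming equal allocation to the two sequences, 12 receive AZD6140 first, 4 per cohort. In the earlier phase IIa study described in Section 3.2, 163 were exposed and one patient stopped for dyspnea: 1/163 = 0.6%. The other rates below are assumptions. Expected losses are 12p; the chance of at least one among n subjects is 1 − (1 − p)^n.

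| Stopping rate p | Expected lost of 12 | At least one of 12 | At least one of 4 |
|---|---|---|---|
| 1/163 | 0.07 | 1 − (162/163)^12 = 7% | 2.4% |
| 5% | 0.6 | 1 − 0.95^12 = 46% | 18.5% |
| 10% | 1.2 | 1 − 0.90^12 = 72% | 34% |
| 20% | 2.4 | 1 − 0.80^12 = 93% | 59% |

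The last row is only a ceiling. The 20% in Section 3.2 is the share reporting dyspnea at 400 mg, and would apply only if every such subject stopped.

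**3. What it does to the described effect**

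Let a share q be stoppers with mean effect D, and let the others have mean effect d.

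- Everyone kept: qD + (1 − q)d.
- AZD6140-first stoppers lost and replaced in the same sequence by subjects who complete: that half of the set has mean d and the other half keeps the full mean, giving 0.5d + 0.5[qD + (1 − q)d]. The error is −q(D − d)/2.

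Illustration with assumed values, q = 10%, effects in breaths/min:

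- D = 4, d = 1: full mean 0.4 + 0.9 = 1.30; set mean 0.5 + 0.65 = 1.15. Toward zero.
- D = 1, d = 1: 1.00 and 1.00. No bias.
- D = 0, d = 1: 0.90 and 0.95. Away from zero.

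Worst case for one cohort: individual effects are normal with SD τ, and the one subject lost is the largest responder of eight. The expected maximum of eight standard normal values is about 1.42, so the mean of the other seven falls by 1.42τ/7 ≈ 0.20τ. Losing the two largest (the second is about 0.85) lowers the mean of the other six by (1.42 + 0.85)τ/6 ≈ 0.38τ.

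**The case against.** The strongest reply is that the route out is narrow and the stakes are modest. Discontinuation under Section 3.3.5.1 needs dyspnea that is moderate to severe and persists for 2 weeks. Section 3.1.2 says that dyspnea should settle before Period II, which is weaker than a bar. Replacement is permitted, not required. In the earlier study most reports were mild and resolved on continued dosing. The study is descriptive, and no test or decision rule hangs on this set. Dosed subjects stay in the safety set, so their adverse events are reported, and a respiratory rate appears under vital signs in Section 4.4.9.2. All of this stands, and it limits the likely size.

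It does not justify the rule. Minute ventilation, spirometry and both dyspnea scales are collected as pharmacodynamic measurements (Section 4.3), and the safety summaries in Section 6.4.3.4 do not name them. Section 3.4.4.2 has evaluability settled before unblinding, but blinding does not remove selection on outcome.

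Four stronger readings are tempting and not supported:

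- That every subject who stops for dyspnea disappears. A placebo-first subject who stops during Period II may qualify.
- That bias toward zero is established. Section 3.2 allows differing sensitivity to the sensation, so dyspnea need not track respiratory rate or ventilation.
- That the sequences become unbalanced and treatment means absorb period effects. Same-sequence replacement largely answers this, and every subject in a both-periods set contributes to both treatments.
- That the dyspnea rates quoted from the earlier study predict the loss. They count reports, not stops.

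**Conclusion.** The point holds in limited form. Section 6.4.2.1 removes AZD6140-first subjects who stop for dyspnea before Period II from the primary respiratory displays and from the listings, and permitted replacement can hide that. The selection is related to the outcome. Its direction is toward zero only if stoppers have the larger respiratory effects, which fits the respiratory-drive hypothesis but is not guaranteed.

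The size is uncertain. The chance that at least one of 12 is lost runs from about 7% at the earlier study's rate to 72% at an assumed 10%. The lower figure pools all AZD6140 regimens of that study in a different population; the loading dose and the respiratory patients here could raise it, but the protocol gives no rate for them. With eight per cohort, one subject is an eighth of the evidence: about 0.20τ in the worst case, less if the stopper is not the largest responder. These figures assume equal allocation, independent stopping and, for the last, normally distributed individual effects.

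**What to change.** In Section 6.4.2.1, define the pharmacodynamic set as all dosed subjects with at least one post-dose respiratory measurement in either period. List every such subject, including those later replaced, and say what makes a measurement evaluable. Show the two-period completers as a supporting within-subject display.

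The cost is one paragraph here and matching text in the SAP, which Section 6.4.1 says is finalized before database lock. No new data are needed. The downside is that raw treatment summaries may rest on unequal numbers of subjects; the completer display addresses that. A model with treatment, period and subject terms would also use the one-period subjects, but is optional in a study that plans no formal analysis.
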